11.5.4.5 Recording of adverse events

AEs must be recorded in the AE Log of the eCRF. The Investigator must provide information on the AE, preferably as a diagnosis or at least as signs and symptoms; start and end dates, start and end time; intensity; causal relationship to IP and comparators, action taken, and outcome. If the AE is serious, this must be indicated in the eCRF.

AEs, including out-of-range clinically significant clinical safety laboratory values, must be recorded individually, except when considered manifestations of the same medical condition or disease state; in such cases, they must be recorded under a single diagnosis.

11.5.4.6 Assessment of seriousness

The Investigator must assess and document the seriousness (serious or non-serious) of each AE using the definitions in Section 11.5.4.2. If the event is assessed as serious it must be reported as an SAE by the Investigator to the Sponsor according to Section 11.5.4.10.

For the seriousness criteria of inpatient hospitalization or prolongation of existing hospitalization to be fulfilled, the AE requires at least an overnight admission (24 hours) or prolongs a hospitalization beyond the expected length of stay. Emergency room visits that do not result in admission to the hospital should be evaluated for one of the other serious outcomes.

Planned hospitalizations or surgical interventions for a condition that existed before the subject signed the ICF, and that did not change in intensity, are not SAEs.

If there is any doubt as to whether an AE meets the definition of an SAE, a conservative approach will be taken, and the AE will be reported as an SAE.

11.5.4.7 Assessment of intensity

The grading of the intensity of AEs will follow the common terminology criteria for adverse events (CTCAE) v5.0 [17]. Grade refers to the severity of the AE. The CTCAE displays Grades 1 through 5 with unique clinical descriptions of severity for each AE based on this general guideline.

The Investigator must assess the intensity of an AE using the following definitions, and record it in the AE Log of the eCRF:

- **Grade 1** Mild; asymptomatic or mild symptoms; clinical or diagnostic observations only; intervention not indicated.
- Grade 2 Moderate; minimal, local, or non-invasive intervention indicated; limiting age-appropriate instrumental activities of daily living (ADL)*.

CONFIDENTIAL 50(76)

Grade 3 Severe or medically significant but not immediately life-threatening;

hospitalization or prolongation of hospitalization indicated; disabling; limiting

self- care ADL**.

Grade 4 Life-threatening consequences: urgent intervention indicated.

Grade 5 Death related to AE.

*Instrumental ADL refers to preparing meals, shopping for groceries or clothes, using the telephone, managing money, *etc*.

**Self-care ADL refers to bathing, dressing, and undressing, feeding self, using the toilet, taking medications, and not bedridden.

11.5.4.8 Assessment of causal relationship

The Investigator must assess the causal relationship between an AE and the use of the IP and comparators using the definitions below. Each assessment should be recorded in the AE Log of the eCRF.

Probable The event has a strong temporal relationship to the IP and comparators, or

recurs on re-challenge, and another etiology is unlikely or significantly less

likely.

Possible The event has a suggestive temporal relationship to the IP and comparators,

and an alternative etiology is equally or less likely.

Unlikely The event has no temporal relationship to the IP and comparators or is due

to underlying or concurrent illness or effect of another drug (i.e., there is no

causal relationship between the IP, and the event).

An AE is considered causally related to the use of the IP and comparators when the causality assessment is probable or possible.

11.5.4.9 Outcome of adverse event

The Investigator must assess the outcome of an AE using the definitions below and record it on the AE Log of the eCRF.

Recovered/resolved The subject has recovered completely, and no symptoms remain.

Recovering/resolving The subject's condition is improving, but symptoms still remain.

Recovered/resolved with

sequelae

The subject has recovered, but some symptoms remain (e.g., the subject had a stroke and is functioning normally, but has some

motor impairment).

Not recovered/not

resolved

The subject's condition has not improved, and the symptoms are

unchanged (e.g., atrial fibrillation has become chronic).

Fatal

Unknown

CONFIDENTIAL 51(76)

11.5.4.10 Action taken with investigational product

The Investigator must document the action taken with the IP using one of the options "Dose not changed", "Drug interrupted", "Drug withdrawn", "Not applicable", or "Unknown", and record it on the AE Log of the eCRF.

11.5.4.11 Reporting of serious adverse events

The Investigator must report SAEs within **24 hours** of awareness to the Sponsor or its designee, this includes both initial information and any subsequent relevant/significant follow-up information to a previously reported SAE. The primary mechanism for reporting an SAE will be via the eCRF. When the Investigator classifies the event as "serious" in the eCRF, and signs off the event, an automatic e-mail alert is sent to the Sponsor or its designee, and any other pre-defined recipients.

The backup procedure for reporting an SAE in case the eCRF is unavailable, will be via the paper SAE form provided in the Investigator Site File (ISF). The Investigator must fill in the SAE form and send it Sponsor or its designee. The study site must notify the site Monitor via phone or e-mail about the submission of the SAE report. As soon as the site personnel have access to the eCRF, the SAE must be reported electronically as well. The completed, signed, and dated paper SAE form should, within 24 hours, be scanned and delivered via encrypted e-mail or secure file transfer to:

A copy of the SAE paper form must also be delivered via encrypted e-mail or secure file transfer to CTC at:

All available information regarding the SAE must be entered in the AE Log for the specific subject, *i.e.*, AE term, intensity, causality, outcome, seriousness criteria, action taken with IP, a narrative including the Investigators rationale for the causality assessment.

The SAE report will be reviewed by the Sponsor or its designee to ensure that the report is valid. The Sponsor or its designee will acknowledge receipt of the SAE report to the reporting Investigator. For SAEs where important or relevant information is missing, follow-up queries to the site are raised promptly to keep the regulatory reporting timelines.

Sponsor will perform an independent assessment of causality, including a rationale for the assessment. The causality assessment given by the Investigator should not be downgraded by the Sponsor. If the Sponsor disagrees with the Investigator's causality assessment, the opinion of both the Investigator and the Sponsor should be provided with the report.

If any additional information or documentation (*e.g.*, autopsy report) on the SAE is required for Sponsor's assessment of the SAE, the Sponsor or its designee will request this information from the Investigator, and the Investigator is required to promptly respond to the request.

Any subsequent relevant/significant follow-up information to a previously reported SAE must be entered in the AE Log for the specific subject. If the Investigator makes any changes to the assessment of the case *e.g.*, changes in seriousness, causality, or intensity, a justification for the change should be provided in the case narrative. If the SAE report in the eCRF is updated, a new automatic e-mail alert is sent to Sponsor or its designee.

CONFIDENTIAL 52(76)

Detailed information on the SAE handling will be described in a study specific safety management plan.

11.5.4.12 Treatment and follow-up of adverse events

Subjects with AEs that occur during the study must be treated according to daily clinical practice at the discretion of the Investigator.

AEs must be followed-up until resolution or to the last visit (Visit 10), whichever comes first. On the last visit, information on new AEs, if any, and stop dates for previously reported AEs must be recorded (if known). AEs assessed as stable by the Investigator at the last IP use visit will not have to be followed-up until resolution.

It is the responsibility of the Investigator to follow-up on all SAEs until the subject has recovered, stabilized, or recovered with sequelae, and to report to the Sponsor all relevant new information using the same procedures and timelines as those for the initial report. Relevant information includes discharge summaries, autopsy reports, and medical consultation.

11.5.4.13 Procedures in case of pregnancy

In case of pregnancy or suspicion of possible pregnancy, the study IP use must be stopped immediately, and the subject should be withdrawn from the study.

Pregnancy itself will not be regarded as an AE unless there is a suspicion that the IP may have interfered with the effectiveness of the contraceptive medication. However, the outcome of all pregnancies (spontaneous miscarriage, elective termination, normal birth, or congenital abnormality) must be followed-up by the Investigator and the Sponsor and documented even after the subject was discontinued from the study.

All pregnancies must immediately be reported by the Investigator to the Sponsor or designee using the Pregnancy Report Form provided in the ISF. Once known, information on the outcome of the pregnancy must also be reported to the Sponsor or designee using the Pregnancy Report Form.

All events of congenital abnormalities, birth defects and spontaneous miscarriages are SAEs and must be handled and reported as such as described in Section 11.5.4.10.

11.5.4.14 Treatment of overdose

An overdose is a dose in excess of the dose specified for subject in this clinical study protocol (CSP).

Overdosing is not likely to occur in this study since all IPs will be administered as single doses by site personnel under medical surveillance. In cases of accidental overdose, standard supportive measures will be adopted as required.

Overdoses must be documented in the eCRF. An overdose associated with AE will be recorded as the AE diagnosis/symptoms in the AE Log of the eCRF. An overdose without associated symptoms will only be reported in the subject's medical records and documented in the PD log.

CONFIDENTIAL 53(76)

11.6 Assessments related to exploratory endpoints

11.6.1.1 Exploratory subjective parameters

The subjective parameter "product-liking" vs. the subject's usual snus/nicotine product of choice will be assessed at 30 minutes with the MCQ "How much did you like the product compared with your usual snus or nicotine product of choice?" on a 3-point scale:

"1 = To a lesser extent, 2 = To the same extent, 3 = To a greater extent."

The allowed deviation from actual time for the MCQ is outlined in Table 11.1-1.

11.6.1.2 Nicotine and tobacco-specific nitrosamines extraction related to exploratory endpoints

Nicotine extraction related to exploratory endpoint 2 is part of the procedure described in Section 11.5.2 above.

For Part 1 and 3, nicotine extraction (related to exploratory endpoints 6 and 7) will be calculated from analysis of used pouches/loose snus collected by the subject during *ad libitum* use of the subject's own brand Swedish snus (Part 1) and the selected NP product (Part 3).

Used pouches/loose snus will be shipped frozen to Swedish Match for chemical analysis of the extracted amount of nicotine, NNK, and NNN. The Sponsor will purchase the applicable products used by the subjects in Part 1 for chemical characterization of the unused pouches/loose snus at Swedish Match. For pouched products, the calculation of the extracted amount and fraction of nicotine, NNK, and NNN will involve subtracting the average of the pouches used by the subjects from the average of 10 unused pouches. For loose snus users, the calculation is based on a single unused reference portion. The weight of this reference portion is identical to the portion that each user prepares themselves during Part 2.

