The screening visit (*Visit 1*) will take place within 5 weeks prior to start of Part 2 (Visit 4) and will include an eligibility check, including evaluations of smoking and oral tobacco/nicotine use, collection of medical history, a brief physical examination, serology tests, electrocardiogram (ECG), vital signs (pulse rate and blood pressure), height, weight, and body mass index (BMI) assessments. During the screening visit, subjects will complete a nicotine dependence questionnaire. They will also select the Swedish snus product, either a pouch or loose snus, which they will use exclusively during Part 1 of the study. Subjects will purchase this product themselves. The chosen product should be the brand they predominantly used in the past month unless they did not exclusively use a single brand. This selection will determine the nicotine strength and flavor variation, as these factors vary within the same brand. For Part 2 of the study and for chemical analyses, the Sponsor will purchase the selected snus product.

Part 1: Ad libitum use of own brand snus

At Visit 2 (first day of Part 1), eligible subjects will return to the study site to receive collection materials for used pouches, undergo eDiary training, and undergo interviews regarding their health status and medications used.

After Visit 2, subjects will exclusively use their product of choice *ad libitum*, following their regular pattern of use. They will document their consumption via an eDiary (ViedocMe) during a 14-day study period, recording the number of pouches/portions used per day, the estimated usage time per pouch/portion, and whether they opened a new snus can for pouch/portion usage once per day. Also, subjects will collect 4 used pouches/portions on two separate days the first week (Samples A) and on two separate days the second week (Samples B) and store these in a freezer (≤ -18°C). In total, 8 pouches/portions will be collected per week. Subjects will receive instructions on how to collect used pouches/loose snus and will be provided with collection containers for storing them and a cooling bag for transportation of the used pouches to the study site.

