8.1.2 Part 2: single IP use in a 5-way cross-over

At Visit 4, the subjects will return to the study site for the first IP use visit of Part 2.

Subjects shall abstain from tobacco/nicotine products as well as smoking (cigarettes or ecigarettes) for 12 hours prior to each IP use visit (Visits 4 to 8). All IP use sessions will be performed during the morning hours (08:00 to 12:00) to facilitate abstinence.

The IPs will be administered as single pouches/portions in a pre-determined randomized order. Randomization will take place before the first IP use of Part 2.

Subjects will keep the pouch/portion between their lip and gum for 30 minutes and will be instructed not to eat, drink, chew gum, or brush their teeth for 30 minutes before, during, and 30 minutes after the IP use.

After 30 minutes, each used pouch/portion will be collected and frozen (-20°C) pending analysis of residual nicotine content. Unused pouches/portions from the same batch will serve as references and will be stored at -20°C pending analyses.

Blood samples for the assessment of nicotine plasma levels and PK parameters will be collected at pre-defined time points from pre-use to 6 hours after each IP use. The PD effects of the IPs will be determined using pulse rate measurements and subjective parameters (using VAS questions) at the same pre-defined time points as well as a multiple-choice question (MCQ) 30 minutes after IP use.

CONFIDENTIAL 30(76)

AEs will be collected through subject interviews and will also include any AEs reported spontaneously by the subjects, starting from the initiation of IP use (Visit 4), and continuing until the last IP use visit (Visit 8).

Visits 5 to 8 will follow the same schedule as Visit 4. Each visit will be scheduled on separate days, preferably with at least 24 hours between visits. However, it is acceptable to have visits on consecutive days, as long as all 5 visits are not scheduled consecutively.

At the end of *Visit 8*, the subject will receive one can of each of the three moist NP products with varying strengths (6 mg, 11 mg, and 16.6 mg) used in Part 2. Importantly, the subjects will be blinded to the nicotine strength of these three products. The subject will test these at home over 2-3 days to ensure they find a suitable replacement for their own brand snus product to be used in Part 3.

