11.5.2 Nicotine extraction from pouches/portions

Used pouches/portions will be collected after 30 minutes (\pm 1 min) of use for the determination of residual nicotine in the IPs.

All the collected pouches/portions will be frozen within 60 minutes at -20°C. Pouches/loose snus for extraction of nicotine will be analyzed by Swedish Match.

In Part 2, all pouches/portions will be weighed prior to use, as will reference pouches/portions.

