17.7 Analysis of secondary endpoints

17.7.1 In vivo extracted amount and fraction of nicotine (Part 2 only)

The difference between the nicotine content of an unused reference pouch or loose snus portion and the used study pouch/portion will be used to calculate the *in vivo* extracted amount and fraction of nicotine for each IP. Extracted amount and fraction of nicotine will be presented using summary statistics. The amount of nicotine in the reference pouches or loose snus portions and in used pouches or loose snus portions will be presented through descriptive statistics.

In addition, extracted amount and fraction of nicotine will be analyzed exploratively using the same model as described in Section 17.6.1 to quantify estimated differences between products.

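### In Part 1 the extracted amount is measured against a reference that is not tied to the used units, and at the protocol's 24% extraction for loose snus any reference error is multiplied about fourfold (exploratory endpoints 6 and 7)

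*Protocol*

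**What the plan says.** **Source of the Part 1 product.** On the own brand snus used in Part 1, the Synopsis (Methodology) says "Subjects will purchase this product themselves". Section 8.1 repeats this.

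**Source of the Part 1 reference.** Section 11.6.1.2: "The Sponsor will purchase the applicable products used by the subjects in Part 1 for chemical characterization of the unused pouches/loose snus". For pouched products, extraction is obtained by "subtracting the average of the pouches used by the subjects from the average of 10 unused pouches".

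**Loose snus.** Same section: "For loose snus users, the calculation is based on a single unused reference portion". Its weight is set equal to the portion the user prepares in Part 2. Section 10.4 obtains that weight on site by weighing the can before and after one portion is taken. No weighing of the portions used at home is described.

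**Part 2, for contrast.** Section 8.1.2: "Unused pouches/portions from the same batch will serve as references".

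**Use of the result.** Section 17.8.6 averages the extracted amounts per subject and multiplies by units per day to get daily exposure. It analyses this on the principles of Section 17.8.5: Part 3 against Part 1, 90% confidence interval, limits 0.80 to 1.25. Section 17.8.7 makes daily exposure the explanatory variable in all nine biomarker models.

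**The concern.** Extraction is a difference between two contents, so it is only as good as the match between them. In Part 1 the residue comes from cans bought by the subject and the reference from cans bought by the Sponsor. The Visit 3 interview covers product, strength and flavor, but no batch. The eDiary asks daily whether a new can was opened, so more than one can per subject is expected. Nothing described would detect a content difference between the two purchases or correct for it.

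For loose snus there is a second mismatch. Residues of self-sized home portions are set against one reference portion sized on a different occasion.

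Averaging many used units does not remove an error in the reference. Part 3 pouches are supplied by the Sponsor, so the weakness lies on the Part 1 side of the comparison. It therefore enters the self-titration comparison of daily exposure and the intake-biomarker regressions. No SAP can recover batch information or portion weights that were not collected.

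**Working it through.** **Inputs.** Section 6.1 gives an extracted fraction of f = 0.24 for loose snus after one hour. Section 11.6.1.2 fixes 10 reference pouches for pouched products and one reference portion for loose snus. Section 8.1.1 has 4 used units collected on two days in each of two weeks: 4 × 2 × 2 = 16. The size of batch differences and of portion-weight variation is not given, so both are assumed below.

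**Check of the protocol's own figure.** 32.1 g × 24% × 0.8% to 1.0% = 61.6 to 77.0 mg per day. This reproduces the stated 62 to 77 mg and confirms that the 24% acts as the extracted fraction.

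**Error formula.** Let true content be C, the reference C(1 + e) and the residue C(1 − f). The computed extraction is C(1 + e) − C(1 − f) = C(f + e). The true value is Cf, so the relative error is e/f. At f = 0.24 the factor is 1/0.24 = 4.17.

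| Assumed content mismatch e | Error in extracted amount, f = 0.24 |
|---|---|
| 2% | 0.02/0.24 = 8% |
| 5% | 0.05/0.24 = 21% |
| 10% | 0.10/0.24 = 42% |

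**Pouched snus.** The protocol gives no extracted fraction for it. Over an assumed range of f from 0.15 to 0.50, the factor 1/f runs from 6.7 to 2.0, and a 5% mismatch gives an error of 33% to 10%.

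**Against the 0.80 to 1.25 limits.** Take a true Part 3/Part 1 ratio of 1, f = 0.24 on the Part 1 side, and no error in Part 3.
- e = −0.048: Part 1 amount × (0.24 − 0.048)/0.24 = 0.80, so the ratio becomes 1/0.80 = 1.25.
- e = +0.060: Part 1 amount × (0.24 + 0.060)/0.24 = 1.25, so the ratio becomes 1/1.25 = 0.80.

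**Loose-snus portion weight.** Assume a within-user CV of 20%. The mean of 16 home portions then has a relative error of 0.20/√16 = 0.05. The single reference weight keeps its full 0.20. The error per subject is √(0.20² + 0.05²)/0.24 = 0.206/0.24, or about 86%. The reference term alone gives 0.20/0.24 = 83%, so collecting more home portions barely helps.

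**When computed extraction reaches zero.** This needs reference weight = 0.76 × home weight, so home portions 1/0.76 = 1.32 times the reference, about 32% heavier.

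**The case against.** The strongest reply is that the endpoints are exploratory and that every mismatch size above is assumed. Batch differences that are independent across subjects and brands mainly add noise. Section 17.8.5 tests self-titration directly on urinary biomarkers, which use no Part 1 reference. All of this stands and limits the weight of the point. It does not cover errors shared by users of one brand, or a systematic difference between home and on-site portion size; those add bias.

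It can also be said that the protocol never states that the batches differ. That is correct: a different batch is a likely inference from two separate purchases. Section 10.2 does have batch IDs of the investigational products filed, and Table 10.1-1 lists own brand snus for Part 1. But no step obtains the batch from cans the subject bought, and nothing ties the Sponsor's reference purchase to it.

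Three stronger readings are tempting, and the document does not support them.
- **Part 2 weights go unused.** Section 11.5.2 says "In Part 2, all pouches/portions will be weighed prior to use, as will reference pouches/portions", while Section 17.7.1 describes "The difference between the nicotine content of an unused reference pouch or loose snus portion and the used study pouch/portion" with no weight term. A reader might infer that the weights are discarded. The text does not say so: the loose-snus weight is used to size the reference, and a weight term for pouches may be in the SAP.
- **Extraction-normalised AUC and Cmax are biased.** These are Part 2 quantities, with same-batch references and a weight-matched loose portion.
- **The 39% in Section 6.1 describes Part 1 pouches.** It is given for marketed nicotine pouches, not pouched snus.

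**Conclusion.** The concern holds for Part 1 and for exploratory endpoints 6 and 7. As written, the reference is a separate purchase with no batch link to the used units. For loose snus it is also one portion whose weight is a single draw from another occasion. At the protocol's 24% for loose snus the error factor is 4.2, and a systematic reference error of about 5% to 6% is enough on its own to move a true ratio of 1 to an equivalence limit.

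The result rests on three assumptions: the mismatch sizes, the 20% portion-weight CV, and the one-hour 24% applying to ad libitum use. A lower fraction would make the factor larger. For pouched snus, likely the larger group since only 10 to 15 loose-snus users are sought among about 53 subjects, the document gives no fraction, so only the assumed range can be shown.

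A reader should not infer that Part 2 extraction, the primary endpoint or the sample size is affected. The change is worth making because it is cheap and the missing information cannot be recovered later.

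**What to change.** 1. **Part 1 reference.** Have each subject freeze and return unused pouches, or unused loose snus, from the cans sampled, and use these as that subject's reference. At the least, record the batch numbers of those cans and match the Sponsor's reference purchase to them.
2. **Loose snus.** Measure reference content as mg/g in replicate. Multiply by the mean weight of several portions weighed on site, for example during the 24-hour stay at Visit 3, when subjects are using their own snus anyway.

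**Cost.** An instruction and a container at Visit 2, a scale at Visit 3, and some extra assays, because references become per subject instead of per product. Subjects already freeze and return used units at Visit 3, so the logistics exist. On-site portions only approximate home portions, so the second change reduces the loose-snus error without removing it. Both changes must be in place before Part 1 samples are collected.
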